4.2.1. Study-Specific Ethical Design Considerations

The primary ethical concern is that participants enrolled in an intervention cohort will be randomized to receive either active study intervention or placebo for 12 weeks, with no therapeutic benefit for this portion of the study. While patients with Crohn's disease do traditionally benefit from inclusion in clinical studies independent of the assigned therapy and many improve even while on placebo (up to 30-50%), the duration of the placebo-controlled induction period has been limited to the extent possible while still maintaining sufficient scientific rigor for meaningful evaluation of critical endoscopic endpoints. Also, participants will be closely monitored during this 12-week period and will continue to receive existing background therapy for Crohn's disease. Participants with worsening Crohn's disease can discontinue the study intervention at any time, and the study intervention should be discontinued if a participant requires additional therapy for Crohn's disease.

The total blood volume to be collected is considered to be an acceptable amount of blood to be collected over this time period from the population in this study and is described Section 8 of this ISA.

Refer to Section 4.2.1 of the Master protocol PLATFORMPACRD2001 for other study-specific ethical design considerations.

4.3. Justification for Dose

JNJ-67864238 is administered orally for local action in the intestinal tract with very little systemic exposure (absolute bioavailability approximately 0.1% in the rat and approximately 0.03% in the monkey). The human equivalent dose approach and relative in vitro (IC50 for IL 23R) and ex vivo (white blood cell pSTAT3 IC50) potency in preclinical species versus humans was used to select the JNJ-67864238 doses evaluated in the FIH study (PTG-200-01). The JNJ-67864238 doses evaluated in the single ascending dose part were [REDACTED] CCI [REDACTED]; the doses evaluated in the multiple ascending dose part were [REDACTED] CCI [REDACTED]

[REDACTED] The dosage selected for this proof-of-concept study is the highest dosage tested in the FIH study (ie, [REDACTED] CCI [REDACTED]). This dosage also produced consistent fecal JNJ-67864238 concentrations in humans which, on average, greatly

exceed the estimated EC80 concentrations or the 50% probability of obtaining a favorable colonic score shown to be efficacious in a TNBS-induced rat model of colitis.

The FIH study in healthy subjects demonstrated that CCI [REDACTED] are safe and generally well tolerated. After multiple dosing, fecal samples showed that only those subjects administered JNJ-67864238 CCI [REDACTED] had substantially higher (~24-fold) median fecal JNJ-67864238 concentrations than the 15,000 ng/mL threshold target.

In view of these results and to maximize the likelihood of a positive outcome in this study, the JNJ-67864238 dose selected is CCI [REDACTED]. This dose is also supported by a preclinical exposure-response analysis of the efficacy of JNJ-67864238 in treating rats with TNBS-induced colitis, as well as safety data following daily dosing for up to 6 months in rats and 9 months in monkeys.

In summary, a dosage of JNJ-67864238 CCI [REDACTED] is selected for this study, as it is supported by preclinical exposure-response modeling, human safety/tolerability from the FIH study, and the toxicology margins established in the Good Laboratory Practice studies.

4.4. End of Study Definition

The end of the JNJ-67864238 intervention cohort is considered as the last visit for the last participant in the intervention cohort. Refer to Section 4.4 of the Master protocol PLATFORMPACRD2001 for a full description of the end of study definition.

5. STUDY POPULATION

To be eligible to participate in the JNJ-67864238 intervention cohort, potential participants must meet all inclusion and exclusion criteria described in Section 5.1 and Section 5.2, respectively, of the Master protocol PLATFORMPACRD2001, which are also listed below. Potential participants must also meet the additional JNJ-67864238-specific inclusion and exclusion criteria presented in Section 5.1 and Section 5.2 of this ISA, respectively, to participate in the JNJ-67864238 intervention cohort.

Considerations specific to JNJ-67864238 include the following:

- Participants who have failed anti-IL-12/23 and anti-IL-23 agents will be excluded.
- Participants with known allergies, hypersensitivity, or intolerance to JNJ-67864238 or its excipients will be excluded.
- As reactivation of latent tuberculosis (TB) has been reported with systemic IL-23 inhibition, participants with evidence of active or latent TB will be excluded. However, because systemic exposure with JNJ-67864238 is far below that required for a pharmacodynamic (PD) effect, the risk for TB reactivation is expected to be low.

Screening for eligible participants will be performed within 5 weeks before administration of the study intervention. Refer to Section 5.4 of this ISA, Screen Failures, for conditions under which the repeat of any screening procedures are allowed.

The inclusion and exclusion criteria for enrolling participants in the Master protocol PLATFORMPACRD2001 and this ISA are described below. If there is a question about these criteria, the investigator must consult with the appropriate sponsor representative and resolve any issues before enrolling a participant in the study. Waivers are not allowed.

5.1. Inclusion Criteria

Each potential participant must satisfy all of the following Master PLATFORMPACRD2001 protocol and these ISA-specific criteria to be enrolled in the JNJ-67864238 intervention cohort.

Master PLATFORMPACRD2001 protocol inclusion criteria are listed below.

1. Male or female
2. 18 to 75 years of age, inclusive

Disease Characteristics

3. Have Crohn's disease or fistulizing Crohn's disease of at least 3 months' duration, with colitis, ileitis, or ileocolitis confirmed at any time in the past by radiography, histology, and/or endoscopy
4. Have active Crohn's disease, defined as a baseline CDAI score of ≥ 220 and ≤ 450
5. Have evidence of active ileocolonic Crohn's disease as assessed by:
 - a. An SES-CD score ≥ 3 at screening by central endoscopy reading
OR
 - b. An elevated screening CRP (>0.3 mg/dL or 3.0 mg/L) or an elevated screening fecal calprotectin (>250 μ g/mg)
6. A participant with a family history of colorectal cancer, personal history of increased risk of colorectal cancer, age >50 years, or other known risk factor must be up-to-date on colorectal cancer surveillance (may be performed during screening). Adenomatous polyps must be removed before the first administration of the study intervention.

7. A participant who has had extensive colitis for ≥ 8 years, or disease limited to the left side of the colon for ≥ 12 years, must either have had a colonoscopy to assess for the presence of dysplasia within 1 year before the first administration of the study intervention or a colonoscopy to assess for the presence of malignancy at the screening visit, with no evidence of malignancy

Concomitant or Previous Medical Therapies Received

8. Meet the following requirements for prior or current medications for Crohn's disease:
 - a. Has previously demonstrated inadequate response to, loss of response to, or intolerance to an approved biologic therapy (unless otherwise specified in the JNJ-67864238 intervention cohort specific criteria below, ie, anti-TNF α agents [eg, infliximab, adalimumab, certolizumab pegol], anti-IL-12/23 agents [eg, ustekinumab], or anti-integrin agents [eg, vedolizumab]), ie, the Bio-IR population (Appendix 2 of the Master protocol PLATFORMPACRD2001 [Definition of Inadequate Initial Response, Loss of Response, or Intolerance to TNF Antagonist Therapies (Infliximab, Adalimumab, or Certolizumab Pegol), Vedolizumab, or Ustekinumab] and Section 5.2 of this ISA)

OR
 - b. Has previously demonstrated an inadequate response to or failed to tolerate corticosteroids or immunomodulators (ie, 6-MP, AZA, and MTX) but not a biologic, ie, the Bio-NF population (Appendix 3 of the Master protocol PLATFORMPACRD2001, Definitions of Inadequate Response to or Intolerance of Corticosteroids or AZA/6 MP and Corticosteroid Dependence)
9. Therapy for the treatment of Crohn's disease must include at least 1 of the following medications, which should have been maintained at stable doses prior to the baseline (Week 0) visit:
 - a. Oral 5-aminosalicylic acid (5-ASA) compounds
 - b. Oral corticosteroids at a prednisone-equivalent dose ≤ 25 mg/day, or 9 mg/day of budesonide, or 5 mg/day beclomethasone dipropionate
 - c. Antibiotics being used as a primary treatment of Crohn's disease
 - d. Conventional immunomodulators (ie, AZA, 6-MP, or MTX) if participants have been taking them for at least 12 weeks and have been at a stable dose for at least 4 weeks prior to baseline

Laboratory Parameters

10. Have screening laboratory test results within the following parameters:
 - a. Hemoglobin ≥ 8.0 g/dL

- b. White blood cell count (WBCs) $\geq 3.0 \times 10^3/\mu\text{L}$
- c. Neutrophils $\geq 1.5 \times 10^3/\mu\text{L}$
- d. Platelets $\geq 100 \times 10^3/\mu\text{L}$
- e. Serum creatinine $< 1.7 \text{ mg/dL}$
- f. Alanine aminotransferase (ALT) and aspartate aminotransferase (AST) concentrations must be within 2 times the upper limit of the normal range for the laboratory conducting the test
- g. Direct (conjugated) bilirubin $< 1.0 \text{ mg/dL}$

Pregnancy Testing

- 11. A woman of childbearing potential must have a negative highly sensitive serum (β -human chorionic gonadotropin [β -hCG]) pregnancy test result at screening and a negative urine pregnancy test result at Week 0.

Other

- 12. Must sign an informed consent form (ICF) indicating that he or she understands the purpose of, and procedures required for, the study and is willing to participate in the study
- 13. Must sign a separate ICF if he or she agrees to provide optional DNA samples for research (where local regulations permit). Refusal to give consent for the optional DNA research samples does not exclude a participant from participation in the study
- 14. Willing and able to adhere to the lifestyle restrictions specified in this protocol

JNJ-67864238 intervention cohort specific inclusion criteria start with the letter A and are listed below.

- A01. A woman using oral contraceptives must use an additional contraceptive method (above that required in Inclusion Criterion A02).
- A02. A woman must be (as defined in [Appendix 2](#) of this ISA, Contraceptive and Barrier Guidance and Collection of Pregnancy Information)
 - a. Not of childbearing potential
 - b. Of childbearing potential and
 - o Practicing a highly effective method of contraception (failure rate of $< 1\%$ per year when used consistently and correctly) and agrees to remain on a highly effective method while receiving study intervention and until 30 days

after last dose - the end of relevant systemic exposure. Examples of highly effective methods of contraception are located in [Appendix 2](#) of this ISA, Contraceptive and Barrier Guidance and Collection of Pregnancy Information.

- A03. A woman must agree not to donate eggs (ova, oocytes) for the purposes of assisted reproduction during the study and for a period of 30 days after receiving the last dose of study intervention.
- A04. A male participant must wear a condom when engaging in any activity that allows for passage of ejaculate to another person.
- A05. A male participant must agree not to donate sperm for the purpose of reproduction during the study and for a minimum 90 days after receiving the last dose of study intervention.
- A06. It is recommended that participants are up to date on age-appropriate vaccinations prior to screening as per routine local medical guidelines. For study participants who received locally approved (and including emergency use-authorized) COVID-19 vaccines recently prior to study entry, follow applicable local vaccine labeling, guidelines, and standards of care for patients receiving immune-targeted therapy when determining an appropriate interval between vaccination and study enrollment (see also Section [6.5](#) Concomitant Therapy).

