4. STUDY DESIGN

4.1. Overall Design

This ISA is designed to assess the effects of a predominantly gastrointestinal-restricted anti-IL-23R compound for moderately to severely active Crohn's disease. This 12-week Phase 2a study is focused on proof-of-concept and will assess the safety and efficacy of an orally administered high dose of JNJ-67864238 compared with placebo in participants with Crohn's disease. Since the inhibition of the IL-23 pathway has been validated as a mechanism for treating Crohn's disease, a high dose was chosen to assess the efficacy of a locally acting anti-IL-23 inhibitor.

The target population for this intervention cohort is defined in Section 4.1.2 of the Master protocol PLATFORMPACRD2001 (ie, men or women 18 to 75 years of age with moderately to severely active Crohn's disease of at least 3 months' duration, defined as a Crohn's Disease Activity Index (CDAI) score ≥ 220 but ≤ 450 at Week 0, with a Simplified Endoscopic Score for Crohn's disease (SES-CD) score ≥ 3 by central endoscopy read OR an elevated C-reactive protein (CRP; >0.3 mg/dL or 3.0 mg/L) or elevated fecal calprotectin (>250 μ g/mg). In this intervention cohort, however, participants with a screening SES-CD score <3 who have an elevated CRP or elevated fecal calprotectin will be limited to 20% of the participant population.

Participants may be biologic intolerant or refractory (Bio-IR) or biologic nonfailures (Bio-NF) populations as defined in Section 4.1.2 of the Master protocol PLATFORMPACRD2001.

A target of 90 Bio-IR and Bio-NF participants will be randomized to receive JNJ-67864238 CCI [REDACTED] or placebo in a 3:2 ratio using permuted block randomization, stratified by baseline CDAI score (≤ 300 , >300) and biological refractory status (Bio-IR, Bio-NF). The treatment arms for this study will be as follows:

- JNJ-67864238 CCI [REDACTED] (N=54)
- Placebo (N=36)

Of note, the sample size has been chosen to assess a level of efficacy consistent with that observed with systemically available biological therapies for Crohn's disease (Section 2.1 of this ISA).

There is 1 database lock (DBL) planned at the end of this intervention cohort. In addition, there will be a planned Interim Analysis (IA) to enable early termination of the intervention cohort if JNJ-67864238 (CCI [REDACTED]) is futile. Additional ad hoc IA(s) may be conducted if deemed necessary. No DBLs are planned for any of the IA(s).

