9.2.2.2. Decision-Making Specifics at the Completion of the Intervention Cohort	Futility criteria for the change in SES-CD were updated.	The futility criteria were corrected for internal document consistency.
9.5. Interim Analysis	Text was added to indicate that the study team will remain blinded at the Interim Analysis.	The text was updated to clarify that the study team will not be unblinded for the Interim Analysis.
4.1. Overall Design; 5.1. Inclusion Criteria	The units for fecal calprotectin were changed from >250 mg/mL to >250 µg/mg.	The units for fecal calprotectin were corrected.
5.2 Exclusion Criteria	Duplication of exclusion criteria #A05 was corrected.	The number A05 was used twice and was corrected to sequential numbering.
6.2. Preparation/Handling/Storage/Accountability	Text regarding the disposition of needles and syringes was removed.	Since JNJ-67864238 is an oral intervention, the text is not applicable.
7.1. Discontinuation of Study Intervention	Text regarding severe injection-site or infusion reactions was removed.	Since JNJ-67864238 is an oral intervention, the text is not applicable.
1.2 Scheme; 1.3 Schedule of Activities	The Patient's Global Impression of Change (PGIC) at Week 0 was removed.	PGIC is not applicable at Week 0.
Throughout the protocol	Minor grammatical, formatting, or spelling changes were made.	Minor errors were noted.

Amendment 1 (14 August 2019)

Overall Rationale for the Amendment: To update the protocol with a newly assigned EudraCT number to allow for re-submission of a request for the Voluntary Harmonisation Procedure (VHP) in the European Union.

Section number and Name	Description of Change	Brief Rationale
Title page	Replacement of the previous EudraCT number (2018-000649-38) with a newly assigned EudraCT number (2019-003335-37).	To allow the re-submission of a request for the VHP for the assessment of the Clinical Trial Authorisation application in the European Union, following rejection of the initial VHP application for administrative reasons.
10.7, Appendix 7 Protocol Amendment History	Update text to indicate that the Protocol Amendment Summary of Changes Table for this current amendment is located before the Table of Contents.	To update the amendment history to indicate that there are amendments for this protocol.

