### 5.7.8. Definition of Subgroups

Subgroups of interest in this study include but not limited to:

1. Population
  - a. BIO-IR vs BIO-NF
2. Demographics at baseline:
  - a. Age ( $\leq$  median age,  $>$ median age)
  - b. Sex (male, female)
  - c. Race (White, non-White)
  - d. Weight at baseline ( $\leq$  median,  $>$  median;  $\leq$  1st quartile,  $>$ 1st quartile and  $\leq$  2nd quartile,  $>$ 2nd quartile and  $\leq$  3rd quartile,  $>$ 3rd quartile)
  - e. Center location (North America, Rest of World)
3. Disease characteristics at baseline:
  - a. Crohn's disease duration ( $\leq$  5 years,  $>$  5 years to  $\leq$  15 years, or  $>$  15 years)
  - b. Involved gastrointestinal areas (ileum only, colon only, ileum & colon)
  - c. CDAI score ( $<$ 300,  $\geq$ 300 )
  - d. CRP ( $\leq$  3 mg/L,  $>$  3 mg/L)
  - e. Fecal Calprotectin ( $\leq$ 250  $\mu$ g/g,  $>$  250  $\mu$ g/g)
4. Concomitant Crohn's-disease medication at baseline:
  - a. Oral corticosteroids (including budesonide and beclomethasone dipropionate) (receiving, not receiving)
  - b. Oral 5-ASA compounds (receiving, not receiving)
  - c. Immunomodulators (6-MP/AZA/MTX) (receiving, not receiving)
  - d. Oral corticosteroids (including budesonide and beclomethasone dipropionate) and Immunomodulators (receiving, not receiving)
5. Other:
  - a. Current fistula at baseline (yes, no)

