**Table 5: Demographic and Baseline Disease Characteristic Variables**

Continuous Variables:	Summary Type
Age (years)	Descriptive statistics (N, mean, standard deviation [SD], median and range [minimum and maximum], and IQ range).
Weight (kg)	
Height (cm)	
Crohn's Disease Duration (yrs)	
CDAI	
PRO-2 (defined as the sum of the abdominal pain and stool frequency subscores of the CDAI score)	
SES-CD	
CRP Concentration (mg/L)	
Fecal Calprotectin (mg/kg)	
Categorical Variables	
Race ([White, Black or African American, Asian, American Indian or Alaska Native, Native Hawaiian or Other Pacific Islander, Other, Not Reported and Unknown])	
Sex ([Male, Female])	
Involved GI areas ([Ileum only, Colon only, Ileum and colon, Proximal gastrointestinal tract, and Perianal])	
Extra intestinal manifestations ([Absent, Present])	
Endoscopic disease severity (SES-CD score) ([Remission (0-2), Mild inflammation (3-6), Moderate inflammation (7-16) and Severe inflammation (>16)])	
Abnormal CRP (>3 mg/L) ([Yes, No])	
Abnormal fecal calprotectin (>250 mg/kg) ([Yes, No])	
Crohn's disease complications (Intra-abdominal abscess, Sinus tracts /perforation, Fistula, Bowel Strictureing]	

Study Day and Relative Day: Study Day 1 or Day 1 refers to the day of the first study agent administration on or after the randomization date. All efficacy and safety assessments at all visits will be assigned a day relative to this date.

Study day or relative day for a visit is defined as:

- Visit date - (date of Study Day 1) +1, if visit date is  $\geq$  date of Day 1
- Visit date - Date of Day 1, if visit date < date of Day 1

There is no 'Day 0'.

Baseline: Baseline is defined as the last observation prior to the first study agent administration unless otherwise specified.

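### The fecal calprotectin entry threshold is 250 µg/mg in the protocol but 250 µg/g in the SAP, a 1000-fold conflict that affects only entrants relying on calprotectin alone

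*Protocol*

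**What the plan says.** Criterion 5 in protocol Section 5.1 asks for evidence of active ileocolonic disease by one of two routes. Route 5a is an SES-CD of at least 3 "at screening by central endoscopy reading". Route 5b is a biomarker route: "An elevated screening CRP (>0.3 mg/dL or 3.0 mg/L"), or "an elevated screening fecal calprotectin", with the cut-off set at >250 µg/mg. Section 4.1 repeats the biomarker alternative ("or elevated fecal calprotectin") with the same µg/mg unit, and limits participants with a screening SES-CD below 3 to 20% of the cohort. Section 5 permits no waivers of the entry criteria.

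The SAP carries the number 250 in three places:

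- Section 5.3.2.1, population of the primary estimand: >250 µg/g.
- Section 5.7.8, "Fecal Calprotectin" subgroup: ≤250 against >250 µg/g.
- Appendix 3, Table 5: "Abnormal fecal calprotectin (>250 mg/kg").

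Section 5.3.2.1 then sends the reader to the protocol for the complete entry criteria.

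**The concern.** The same number is attached to units that differ by three orders of magnitude, and in the protocol it is an operative entry rule. Two consequences follow for a candidate with SES-CD <3 and non-elevated CRP.

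- **Protocol read literally.** The candidate would need calprotectin above a quarter of the stool sample by mass, so the calprotectin route in 5b is closed in practice.
- **Site applies 250 µg/g.** The candidate enters against the written criterion. SAP Appendix 4 tabulates participants who entered without satisfying the entry criteria as major deviations. Sensitivity Estimator 1 (SAP 5.3.3.2) excludes participants with major deviations, and the per-protocol set (SAP Section 4) requires compliance. The unit in force therefore decides how these participants are classified.

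The estimand population is also described by two rules: the SAP's own figure, and the protocol criteria to which it refers.

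**Working it through.** The threshold is a stated constant, so the check is a unit conversion and a side-by-side reading.

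**Inputs**

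- Protocol 4.1 and 5.1 (criterion 5b): 250 µg/mg.
- SAP 5.3.2.1 and 5.7.8: 250 µg/g.
- SAP Table 5: 250 mg/kg.
- Protocol 5.1, CRP cut-off in the same criterion: 0.3 mg/dL, also given as 3.0 mg/L.
- Protocol 4.1: target of 90 participants, with a 20% cap on SES-CD <3.

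**Step 1: convert everything to µg/g.**

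- Protocol: 250 µg/mg × 1000 mg/g = 250,000 µg/g.
- SAP Table 5: 250 mg/kg × 1000 µg/mg ÷ 1000 g/kg = 250 µg/g, so all three SAP statements agree.
- Ratio: 250,000 ÷ 250 = 1000.

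**Step 2: express as a mass fraction** (1 g = 1,000,000 µg).

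- Protocol: 250,000 ÷ 1,000,000 = 0.25, or 25% of the sample.
- SAP: 250 ÷ 1,000,000 = 0.00025, or 0.025%.

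**Step 3: check the neighbouring unit.** For CRP, 0.3 mg/dL × 10 dL/L = 3.0 mg/L, which matches. The fault in criterion 5b is confined to calprotectin.

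**Step 4: is the unit a text-extraction slip?** It appears in two current protocol sections. The amendment history (Appendix 9, Amendment 2) records a deliberate change from mg/mL to µg/mg in both, with the rationale "The units for fecal calprotectin were corrected". The log is used here only to show that µg/mg is what the protocol intends to print. The change hardly moved the threshold. The documents give no stool density; at an assumed 0.9 to 1.1 g/mL, 250 mg/mL is 250,000 ÷ 1.1 ≈ 227,000 to 250,000 ÷ 0.9 ≈ 278,000 µg/g.

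**Step 5: who is exposed?** Criterion 5 is met by SES-CD ≥3, or raised CRP, or raised calprotectin. The unit matters only when the first two fail. Those participants fall within the SES-CD <3 group, capped at 0.20 × 90 = 18. That group also contains participants who qualify on CRP, so the range is 0 to 18.

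**Step 6: what in the analysis uses the threshold?**

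- The full analysis set is everyone randomised and dosed (SAP Section 4).
- The primary MMRM (SAP 5.3.3.1) uses treatment, time, baseline CDAI and biologic status.
- The decision rules (protocol 9.2.2) use CDAI and SES-CD.
- The power statement (SAP Section 3) rests on a difference of 60 and an SD of 93 in CDAI change.

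None of these involves calprotectin.

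**The case against.** The strongest reply is that a threshold of 25% of sample mass is so plainly wrong that no site would follow it. The number 250 is common to both documents, the SAP is consistent with itself, and Section 5 of the protocol tells investigators to settle questions about criteria with the sponsor before enrolling. Nothing in the documents shows that anyone was wrongly included or excluded. This lowers the likely harm. It does not remove the conflict, because if sites do use 250 µg/g, the rule in use is not the rule written, and no waiver is available to cover the gap.

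Three stronger readings are tempting, and the documents do not support them:

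- **That calprotectin can never satisfy 5b as written.** No assay range or physiological limit is given. The literal value is implausible, but unattainability is an inference.
- **That 18 participants are affected.** Eighteen is the ceiling for all SES-CD <3 entrants. The calprotectin-only subset is not reported and could be empty.
- **That the SAP's subgroup and Table 5 cut-offs set a rival entry rule.** They are descriptive baseline categories. Only the estimand population in SAP 5.3.2.1 restates eligibility.

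It is also fair to say that criterion 5 is relisted from the Master protocol, which is not available here. The fault may be a transcription slip in this document, or it may start there.

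**Conclusion.** The conflict is real and the entry criterion is wrong as written. The factor of 1000 is exact and needs no assumption. That µg/g is the intended unit is an inference, resting on the three concordant SAP statements and on the implausible mass fraction in the protocol.

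The reach is narrow: only entrants with SES-CD <3 and non-elevated CRP who rely on calprotectin, between 0 and 18 of 90. Candidates turned away at screening under a literal reading would be additional, and the documents give no basis for counting them. The effects on analysis are limited to deviation and per-protocol classification and to the description of the estimand population. The full analysis set, primary model, decision rules and power stand. The point deserves correction because it sits in an operative entry rule and costs almost nothing to put right, not because it threatens the main result.

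**What to change.** - Reconcile the calprotectin unit in protocol Section 4.1 and inclusion 5b with SAP 5.3.2.1. The evidence above points to µg/g.
- Use one unit throughout both documents, including SAP Table 5, where mg/kg is equivalent but invites confusion.
- Check the matching Master protocol text (criterion 5, and Section 4.1.2, which Section 4.1 cites for the target population) and amend it if it carries the same unit.
- Confirm from screening records which unit was applied, whether any candidate failed screening because of it, and that deviation and per-protocol classification use the reconciled threshold.

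The text change is one unit in two protocol places, by amendment or clarification letter, plus a Master protocol change if needed. The screening check is confined to participants and candidates with SES-CD <3 and non-elevated CRP. There is no effect on design, sample size or analysis model.
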